Overall Analyses will include (1) evaluation to determine data quality, (2) creation of constructed variables and determination of variable distributions, (3) applying tests of parametric statistical assumptions wherever appropriate, (4) preliminary (generally bivariate) testing of hypotheses, (5) consideration of potential covariates to build into the statistical models to increase the probability of detecting treatment effects if they exist, and (6) development and elaboration of multivariate models. SPSS software (V25, IBM, Armonk, NY, USA) will be used for all statistical analyses (significance, $p < 0.05$). [name] will perform all statistical analyses and work with Drs. [name] and [name] on statistical analyses.

Aims 1, 2: In order to evaluate outcomes of the intervention, we will first determine the melatonin suppression for each condition by comparing melatonin levels collected during the dim-light control week to those at the same time in the experimental conditions' weeks. We will then perform a mixed-model analysis of variance (ANOVA), with lighting distribution (on-axis vs. off-axis) and spectrum (blue light vs. green light) serving as the within-subjects factors, and MPOD group (high MPOD > 0.5 vs. low MPOD < 0.3) and cognitive status (MoCA scores) (healthy vs. MCI participants) serving as the between-subjects factors. Mixed model analyses allow for different numbers of observations for different subjects (e.g. if there are dropouts). As sample size and its associated degrees of freedom allow, we will also adjust for covariates that may be associated with outcome measures, such as retinal illuminance, gender, season and any medication load. Within the limits of the sample, we will explore treatment-covariate interactions for each participant-level covariate. If strong interactions are observed, it will suggest that a future study could possibly be stratified on the given factor. To further assess the impact of MPOD on individual light sensitivity, a Pearson correlation coefficient will be calculated between melatonin suppression and MPOD values recorded across MCI patients and healthy older adults. We hypothesize a negative correlation, wherein higher MPOD values will be associated with lower suppression.

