The daily pattern of light and dark reaching our retinas is the primary *zeitgeber* that regulates distinct biological processes by setting the timing of the endogenous circadian pacemaker in the suprachiasmatic nucleus (SCN) in accordance with Earth's 24-h solar day. Melatonin is produced by the pineal gland at night in dark conditions and is known as the "darkness hormone." In humans, melatonin is used as a marker of the timing of the biological clock and its production is ceased by exposure to light at night, which is one of the main reasons melatonin is used as an outcome measure in experiments designed to understand circadian phototransduction mechanisms in humans.^{7,8} Circulating melatonin levels change in a graded manner to variations in spectrum, amount, distribution, duration, and timing of light exposure. It is therefore imperative that a complete understanding of these lighting characteristics be developed so that: (1) the most effective lighting is used for therapy and (2) the most appropriate and effective light is installed in buildings. The latter application is particularly significant because senior housing lighting is typically dim and constant, which could be a reason why sleep disturbances are so much more common in older adults, including those with Alzheimer's disease and related dementias (ADRD) who are living in more controlled environments. Much is already known about the absolute and spectral sensitivities^{9,10,11} of acute melatonin suppression, but not much attention has been given to the effect of light's spatial characteristics (distribution) and phenotype (macular pigment optical density or MPOD). The present application will characterize how light distribution on the retina and MPOD affect melatonin suppression. **We hypothesize that light incipient on the retina in central vision (i.e., at the fovea) will be more effective at suppressing melatonin than light reaching the periphery of the retina, and that melatonin suppression will be inversely correlated with MPOD.** We further hypothesize that, compared to age-matched controls, mild cognitive impairment (MCI) patients will have lower MPOD than age-matched controls. Finally, we will explore the relationship between MPOD and cognition and the feasibility of using MPOD as a biomarker of individual light sensitivity. The following aims will be investigated:

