Macular pigment optical density (MPOD): In addition to the photoreceptors, the density of the short-wavelength optical radiation attenuating macular pigment has also been shown to vary across the retina. Typically, the concentration of the macular pigment is highest at, or near, the fovea and rapidly decreases with an increase in eccentricity. In healthy adults, MPOD has been shown to vary by almost one log unit (0.1-1.0), and that the within population MPOD variance can be largely explained by factors such as diet, age, and genetics⁴¹. *Therefore, MPOD may be used as a biomarker for individual sensitivity to light treatment.*

Relationship between macular carotenoids and cognitive function: The macular carotenoids lutein (L) and zeaxanthin (Z) preferentially accumulate in the central retina where their concentrations can be reliably assessed by measuring MPOD.⁴² L and Z carotenoids have been shown to breech the blood-brain barrier and accumulate in various diffuse brain regions, with an especially high correlation reported between retinal L and Z levels and those estimated in occipital brain areas.⁴³⁻⁴⁶ In other words, a close relationship between the macular carotenoids (and the retina itself) and the rest of the central nervous system⁴⁷⁻⁵⁰ has enabled the researchers to employ MPOD as a proxy for neural L and Z concentrations.⁴⁵ More importantly, a number of studies have shown that higher concentrations of L and Z, as measured by higher MPOD values, have been significantly associated with improved cognitive performance,^{47,51-57} potentially by strengthening neural structure and augmenting neural efficiency.⁴⁹ For example, a recent study has reported significantly lower performance on global measures of cognitive functioning (based on Mini-Mental Status Exam and Montreal Cognitive Assessment outcomes) in older adults with low MPOD values.⁵⁸ MPOD has also been associated with other cognitive functions regulating attention, visual memory, learning, and cognitive flexibility measuring subject's

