The results of the proposed research would inform the development of light-delivery methods to promote circadian entrainment and improve sleep consolidation in patients afflicted with MCI and ADRD, who typically spend a significant amount of time indoors. Several studies in the literature have associated AD with an increase in circadian disruption.^{61,62} Prior work by [name] (PI) has shown that appropriately timed light exposure can increase sleep efficiency (Fig. 1), decrease agitation, and even limit cognitive decline in the ADRD population,⁶³ but the light delivery method and strategy has been identified as one of the greatest challenges for successful treatment. Results from the proposed research are also important to this specific application, as past studies have reported significantly lower MPODs in MCI and ADRD populations.⁶⁴ Finally, we will be able to better understand whether MPOD affects cognition and explore the possibility that MPOD could be used as a biomarker for individual sensitivity to light, allowing for the development of individualized light treatment prescriptions to more effectively entrain the circadian system, thus, improving sleep and cognition.

Following advancements in LED technology that allow more dynamic distribution patterns for light sources, the proposed work marks an important shift in approach moving beyond the conventional "light at the cornea" for circadian lighting to "light at the retina." The meticulously planned study will test a novel strategy of whether modulating lighting distribution at the eye provides a more efficient way to manipulate circadian stimulus delivered, compared to amount or spectral modifications for light sources, which often are governed by requirements to satisfactorily perform visual tasks. The state-of-the-art custom-built lighting apparatus will allow us to selectively involve and study interaction of MPOD with the varying lighting characteristics (spectrum, distribution), which is unique as no prior studies have examined the correlation between MPOD and melatonin suppression. Lastly, the target spectra for the narrowband sources have been selected so that photic stimulus incident on the retina will be attenuated by the macular pigment (peak absorbance = 460 nm) only for the blue light and not the green light exposures proposed for the study (see Experimental Conditions).

Approach

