Participant selection: Following IRB approval, we will recruit 24 MCI participants and 24 healthy, age-matched controls through e-mail notices, posters, and word-of-mouth. MPOD will be assessed at the recruitment stage for all subjects to determine their initial eligibility, which will require subjects to fit into one of 2 distinct groups (low: MPOD < 0.3, high: MPOD > 0.5). **Eligible participants will be MCI or mild AD patients who are 55 years and older.** We will work with our physician collaborators in the area (who are currently working with the PIs in 3 other R01s) to perform the pre-selection diagnosis according to the following **pre-selection criteria:** Participants must be diagnosed by their physician with amnestic MCI or mild AD. Subjects in the control group will have normal cognition. Study participants who meet the following inclusion and exclusion will discuss informed consent for study participation: **Inclusion criteria:** Those taking antidepressants will be included, but type of medicine and dosage intake will be monitored. There will be no exclusions based gender, race, and ethnicity. Participants must also not meet the following **Exclusion criteria:** Presence of another brain disease that fully explains the dementia (extensive brain vascular disease, Parkinson's disease, dementia with Lewy bodies, traumatic brain injury, or multiple sclerosis); residence in a skilled nursing facility or long-term care; indication for psychiatric hospitalization or acute suicidality in the opinion of the physician; major organ failure (e.g., kidney failure); or uncontrolled generalized disorders such as hypertension or diabetes. Exclusion criteria will also extend to obstructing cataracts, macular degeneration, and blindness. Those taking over-the-counter melatonin, prescription sleep medication or beta blockers will be excluded. We will review the participants' ophthalmologic tests during selection and exclude those who have undergone

[figure not shown]

Fig. 2. Correlation between MPOD and melatonin suppression showing pooled data from a series of within-subjects nighttime studies. Each yellow diamond corresponds to suppression data for an individual subject. The black line corresponds to the best fit linear regression model. All subjects underwent a 1-h exposure to white light sources with CCTs ranging

[figure not shown]

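### Enrolment is fixed by diagnosis only, with no target per MPOD × cognitive-status cell, so the 2×2 between-subjects design may be strongly unbalanced

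*Combined protocol and SAP*

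**What the plan says.** Under Approach, Participant selection: "we will recruit 24 MCI participants and 24 healthy, age-matched controls through e-mail notices, posters, and word-of-mouth". MPOD is measured at recruitment to settle initial eligibility, "which will require subjects to fit into one of 2 distinct groups (low: MPOD < 0.3, high: MPOD > 0.5". People between the two cut-offs are not enrolled. Controls are matched on age. The documents supplied give no quota, cap or stratification by MPOD.

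Under Data and Statistical Analyses, Aims 1, 2, the mixed-model ANOVA has two between-subjects factors. One is "MPOD group (high MPOD > 0.5 vs. low MPOD < 0.3"; the other is "cognitive status (MoCA scores) (healthy vs. MCI participants) serving as the between-subjects factors". In addition, "a Pearson correlation coefficient will be calculated between melatonin suppression and MPOD values recorded across MCI patients and healthy older adults". No adjustment for cognitive status is stated for that correlation.

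The plan expects the two factors to be associated. The opening aims text hypothesises that "mild cognitive impairment (MCI) patients will have lower MPOD than age-matched controls", and Significance and Innovation notes that "past studies have reported significantly lower MPODs in MCI and ADRD populations". The only information on the MPOD distribution is in the Background: "In healthy adults, MPOD has been shown to vary by almost one log unit (0.1-1.0". Sample Size and Estimated Power works per diagnosis group (24 recruited, 19 completers) from an earlier within-subjects study and does not consider the four cells.

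**The concern.** If MCI patients tend to have lower MPOD and the middle of the range is dropped, eligible MCI patients will tend to fall below 0.3 more often than eligible controls do. Nothing in the recruitment rule counters this. The MCI group could fill mostly with low-MPOD people while controls split differently.

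Aim 2 asks how MPOD affects suppression in MCI patients and in controls. An MPOD contrast within MCI needs reasonable numbers in both strata of that group, and the MPOD × status interaction needs all four cells. The pooled Pearson correlation is exposed in another way: if suppression differs between MCI and controls for reasons other than MPOD, part of that difference will appear as an MPOD association. The direction is unclear from the plan. Preliminary Data can be read as saying that older adults with MCI are less sensitive to light, whereas the exploratory hypothesis at the end of the Background expects low-MPOD MCI patients to suppress more under on-axis light.

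Cell balance cannot be restored once recruitment closes. The exclusion of people with low melatonin after the dim-light night could thin a small cell further.

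**Working it through.** **Inputs from the plan.** 24 per diagnosis group; 20% attrition; MPOD cut-offs 0.3 and 0.5. The plan's completer figure reproduces: 24 × 0.80 = 19.2, so 19 per group. There is no planned cell size to reproduce.

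**Assumptions, because the plan gives none.** MPOD is normal with SD 0.15; the control mean is 0.40; the MCI mean is 0.35 (small deficit) or 0.30 (larger deficit); attrition is unrelated to MPOD.

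**Step 1: expected split among eligible people.** P(low) = Φ((0.3 − μ)/0.15); P(high) = 1 − Φ((0.5 − μ)/0.15).

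| Group, mean | P(low) | P(high) | High share of eligible | Low / high of 19 |
|---|---|---|---|---|
| Controls, 0.40 | 0.25 | 0.25 | 50% | 9.5 / 9.5 |
| MCI, 0.35 | 0.37 | 0.16 | 30% | 13.3 / 5.7 |
| MCI, 0.30 | 0.50 | 0.09 | 15% | 16 / 3 |

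**Step 2: correlation between the factors.** With MCI low and high counts a, b and control counts c, d, phi = (ad − bc)/√[(a+b)(c+d)(a+c)(b+d)].
- MCI mean 0.35: (13.3 − 5.7) × 9.5 / (19 × √(22.8 × 15.2)) = 72.2/353.7 = 0.20.
- MCI mean 0.30: (16 − 3) × 9.5 / (19 × √(25.5 × 12.5)) = 123.5/339.2 = 0.36.

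**Step 3: efficiency of the MPOD main effect and of the interaction.** Both cell-mean contrasts have variance proportional to the sum of 1/n over the four cells, so relative efficiency = (4/9.5)/Σ(1/n), with 4/9.5 = 0.421.
- MCI mean 0.35: Σ = 0.461; 0.421/0.461 = 91%; standard error 1/√0.91 = 1.05 times the balanced one.
- MCI mean 0.30: Σ = 0.606; 0.421/0.606 = 69%; standard error 1.20 times the balanced one.

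In an additive model without the interaction, information is the sum over groups of low × high/19, against 9.5 when balanced. For MCI mean 0.30 it is (2.53 + 4.75)/9.5 = 77%; for 0.35 it is (3.99 + 4.75)/9.5 = 92%.

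**Step 4: MPOD contrast within MCI.** The standard error is proportional to √(1/a + 1/b). Balanced: √(2/9.5) = 0.459. MCI mean 0.35: 0.501, or 1.09 times. MCI mean 0.30: 0.629, or 1.37 times.

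**Step 5: pooled correlation.** If MPOD and suppression are unrelated within each diagnosis group, the pooled correlation equals corr(MPOD, status) × corr(suppression, status). Taking phi as the first term, 20% to 36% of any status–suppression correlation would appear as an MPOD correlation.

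**Step 6: other assumptions.** Eighteen combinations were tried: control mean 0.30, 0.40 or 0.50; MCI deficit 0.05, 0.10 or 0.15; SD 0.15 or 0.20. In 16 of them the smallest expected cell among 19 completers per group is below 5. The two exceptions are control mean 0.40 with deficit 0.05 (smallest cell 5.7 or 6.9). Which cell is thin depends on the control mean. For a deficit of 0.10:
- control mean 0.30: 0.6 to 1.7 high-MPOD MCI completers;
- control mean 0.40: 2.9 to 4.6 high-MPOD MCI completers;
- control mean 0.50: 9.5 high-MPOD MCI completers, and the thin cell is low-MPOD controls, at 2.9 to 4.6.

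**Step 7: effect of a cap.** A 16/8 split among 24 becomes 12.7/6.3 among 19. With controls even, Σ(1/n) = 0.448, efficiency is 0.421/0.448 = 94% and phi is 0.17.

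**The case against.** A reader might infer that the high-MPOD MCI cell will be nearly empty. The documents do not support that. They give only a range for healthy adults, and under the assumptions in Step 6 the expected share of MCI completers above 0.5 runs from close to none to half or more. At the milder end of the main scenario the uncapped plan already keeps 91% efficiency, against 94% with the cap.

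A reader might also infer that MPOD and cognitive status will be confounded. That is too strong for the ANOVA. Both factors are in the model, so each is adjusted for the other and both stay estimable while all four cells are occupied; the cost there is precision. Nor does the MPOD estimate rest overwhelmingly on controls: in the additive model MCI supplies 2.53/7.28 = 35% of the information at MCI mean 0.30 and 3.99/8.74 = 46% at 0.35. The on-axis versus off-axis contrast of Aim 1 is within-subject, so everyone contributes to it whatever the cell mix.

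Other points stand. The study describes itself as exploratory and a feasibility study, so a costly quota needs justifying. A quota would weaken the pooled MPOD–cognition association that Aim 3 seeks. The human subjects' section to which the plan refers for its timeline is not in the supplied documents, so a cell target there cannot be ruled out.

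The plan's remark that mixed models tolerate differing numbers of observations does not answer the point: it concerns observations per subject, such as dropouts, not how many people enter each cell.

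**Conclusion.** The concern holds as a risk of imbalance. Fixing numbers by diagnosis alone, while expecting MPOD to differ by diagnosis, makes an unbalanced and non-orthogonal 2×2 the result that the plan itself predicts, and nothing in the supplied text corrects it. How severe it will be cannot be derived from the documents. With a control mean of 0.40, SD 0.15 and an MCI mean of 0.30 to 0.35, the standard errors of the MPOD main effect and of the MPOD × status interaction rise by 5% to 20%, and that of the MPOD contrast within MCI by 9% to 37%. Other plausible values make the loss larger or smaller, or move the thin cell to low-MPOD controls.

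The pooled MPOD–suppression correlation is the one analysis here where bias, rather than lost precision, is possible. That bias requires suppression to differ by status for reasons other than MPOD.

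**What to change.** 1. In Participant selection, state that within each diagnosis group an MPOD stratum closes when it reaches 16 of 24, leaving at least 8 for the other. Because it applies to both groups, it covers either thin cell. Make it a target that may be relaxed after a pre-stated number of people screened.
2. Adjust the MPOD–suppression correlation for cognitive status, for example as a partial correlation, or report it within each diagnosis group.
3. Estimate the MCI–control difference in MPOD in everyone screened, before the MPOD cut. Report the Aim 3 MPOD–cognition correlations within diagnosis group, or acknowledge the quota's effect on the pooled value.

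**Cost.** This needs a few sentences, no extra participants and no extra tests for those enrolled, since MPOD is already measured at recruitment. The main cost is screening. Under the main assumptions, 24 eligible MCI patients need about 24/0.59 = 41 to 24/0.53 = 45 candidates. Finding 8 with high MPOD needs about 8/0.16 = 50 to 8/0.091 = 88. Under less favourable values it can be far more: with control mean 0.30, SD 0.15 and deficit 0.10, P(high) in MCI is about 0.023 and 8/0.023 is about 350, which is why the relaxation rule is needed. The second cost is a weaker pooled Aim 3 association in the enrolled sample. The figure of 8 is a judgement; a different floor would trade screening against precision in the same way.

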Fig. 3. Relative spectral power distributions of potential narrowband blue light source ($\lambda_{\text{max}} = 451 \text{ nm}$) and green light source ($\lambda_{\text{max}} = 522 \text{ nm}$). Also shown is the relative spectral absorbance of the macular pigment, adapted

cataract surgery and received an intraocular lens coated with ultraviolet- and blue-blocking filters (400-440/440-500 nm). Those with a history of severe photosensitivity dermatitis, severe progressive retinal disease (e.g., macular degeneration), or a permanently dilated pupil (e.g., after certain types of cataract surgery) will also be excluded. Subjects will also be required to maintain a regular sleep schedule (bedtimes no later than 23:00 and wake times no later than 08:00) starting 2 weeks prior to the experimental sessions and continuing throughout the experiment's duration. The experimenters will run the dim-light control condition first, and any subjects who present low nighttime (i.e., at 24:00) melatonin levels will be excluded from the study. This study will conform to the Code of Federal Regulations (CFR) document Protection of Human Subjects, 45 CFR 46, ⁶⁷ and International Ethical Standards. ⁶⁸

Experimental conditions: In addition to a dim-light control condition, participants will be exposed to 2 narrowband sources: blue light ($\lambda_{\max} = 451$ nm) and green light ($\lambda_{\max} = 522$ nm) (Fig. 3), presented in 4 interventions. The 2 interventions for each narrowband source, designated on-axis and off-axis, will have distinct lighting distribution patterns but calibrated to deliver the same targeted levels of circadian light (CL_A) and circadian stimulus (CS) at the eye. ^{60,69} The 4 interventions will target a CS = 0.40 (≈ 27 lux for blue light, ≈ 250 lux for green light) at the participants' eyes and the dim light control will target a CS < 0.1 (< 5 lux of 2700 K light) at the eyes. The 4 lighting conditions will be counter-balanced across all the participants. Over the course of the study, spectral irradiance measurements for the 2 narrowband sources will be performed using a spectrometer (Model USB650, Ocean Optics, Winter Park, FL, USA).

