Lighting apparatus: The on-axis and off-axis lighting interventions will be delivered via RGB color-tunable LED luminaires (model G2, Ketra, Austin, TX), each driven by a satellite link controller (model N3, Ketra) with a touchpad interface (model X1, Ketra) and housed in fixtures that will be placed directly on desks at which

[figure not shown]

Fig. 4. The layout of the desktop luminaires with respect to the participants' eyes during the experiment (left), and the luminaires' configuration when delivering the on-axis and off-axis interventions (right). The circle shown in the center of the luminaires represents a low-power LED that will be used as a simple on-axis visual task to maintain participants line of sight.

the participants will be seated. The luminaires will be covered by spectrally neutral diffusers to eliminate potential glare. The intervention stimulus will be calibrated using a tripod-mounted illuminance meter (Model X-91, Gigahertz-Optik, [name]). The target photometric characteristics of the intervention light stimulus for measures of illuminance, CL_A, and CS following [name] and [name] ⁷⁰, and equivalent melanopic lux (EML) following Enezi, et al. ⁷¹ are shown in Table 1. To ensure consistency of the delivered lighting dose, participants will be required to use a chin rest, optimally adjusted to maintain a fixed distance of 30 in. from the 22 in. x 5 in. (w x h) light-emitting area of the desktop luminaire (Fig. 4). The on-axis intervention will provide an image $\pm 5^\circ$ in width at each participant's eyes. The off-axis intervention will provide an image $\pm 8-20^\circ$ in width at each participant's eyes.

Table 1. Photometric characteristics of the target blue light and green light stimulus calculated following [name] and [name] ⁷⁰ (CS) and Enezi, et al. ⁷¹ (EML)

Experimental condition	Photopic illuminance (lux)	CL _A	EML	Predicted CS
Blue on-axis / Blue off-axis	26.7	473.7	154.0	0.40
Green on-axis / Green off-axis	250.0	473.7	274.0	0.40

Participant measurements and field monitoring procedures:

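### Table 1's blue lux and EML do not fit a single narrowband 451 nm source, and the plan does not say that spectrometer readings set the level

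*Combined protocol and SAP*

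**What the plan says.** - Approach, Experimental conditions: "participants will be exposed to 2 narrowband sources: blue light" peaking at 451 nm, and green light peaking at 522 nm. On-axis and off-axis versions of each are "calibrated to deliver the same targeted levels of circadian light (CL_A) and circadian stimulus (CS) at the eye". The levels are given as: "The 4 interventions will target a CS = 0.40 (≈ 27 lux for blue light, ≈ 250 lux for green light".
- Same section: "spectral irradiance measurements for the 2 narrowband sources will be performed using a spectrometer" over the course of the study. No sentence says that these readings set or correct the level.
- Fig. 3 caption: "Relative spectral power distributions of potential narrowband blue light source". The figure itself is not in the text available to this review.
- Lighting apparatus: the light comes from "RGB color-tunable LED luminaires", and "The intervention stimulus will be calibrated using a tripod-mounted illuminance meter".
- Table 1: blue is 26.7 lux, CL_A 473.7, EML 154.0, CS 0.40. Green is 250.0 lux, CL_A 473.7, EML 274.0, CS 0.40.
- Melatonin Suppression Protocol, Fig. 5: 27 lux is repeated for the on-axis and off-axis conditions.

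**The concern.** Lux and EML are two weightings of the same spectrum, so their ratio is fixed by the spectrum's shape. A stated peak and a narrow width leave little freedom. The photopic curve is low at 451 nm while the melanopic curve is high, so a narrow blue band should give many EML per lux. The printed 5.77 looks too small.

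This matters because the stated calibration instrument reads lux. Where photopic sensitivity is low, a little light outside the band can supply most of the lux reading, so lux is a fragile measure of blue dose. The plan wants equal CL_A and CS across colours and makes spectrum a within-subjects factor in the mixed-model ANOVA (Aims 1, 2). A wrong blue level would bear on the spectrum main effect and on the prediction in Anticipated Outcomes that high-MPOD participants suppress more under green than under blue. The planned retinal-illuminance covariate (luminance times pupil area, in trolands) is photopic, so it would not reveal such an error.

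**Working it through.** **Inputs from the documents.** Peaks of 451 and 522 nm (Experimental conditions); lux, EML and CL_A from Table 1.

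**Assumed, not in the documents.** Standard photopic curve V; melanopic curve M, a 480 nm pigment template filtered by an adult lens (ages 20-45); Gaussian bands with full width at half maximum (FWHM) 2-40 nm; EML scaled to equal lux for an equal-energy spectrum.

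**Formula.** For spectrum E: EML/lux = (∫E·M / ∫M) / (∫E·V / ∫V).

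**1. Printed ratios.** Blue 154.0/26.7 = 5.77. Green 274.0/250.0 = 1.096. Quotient 5.77/1.096 = 5.26.

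**2. Green row as a check.** At 522 nm the method gives 1.00-1.16, which brackets 1.096. With a 32-year lens and FWHM 25-50 nm, 250 lux gives EML 270-277 against 274 printed. The green row reproduces.

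**3. Blue row, same method.**

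| Width at 451 nm | EML/lux |
|---|---|
| FWHM 2-40 nm | 19.6 down to 13.3 |
| FWHM 60 nm | 9.6-10.3 |
| FWHM 80 nm | 6.5-6.9 |
| Printed | 5.77 |

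Lenses of 65-75 years lower the narrowband result only to about 10-14. Replacing V by a 10-degree luminosity curve gives 6.8-9.2, which is 6.8/5.77 = 1.2 to 9.2/5.77 = 1.6 times the printed ratio. The blue-to-green quotient, which does not depend on how EML is scaled, is about 15-24 across the melanopic curves tried (with the standard photopic curve), against 5.26 printed.

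**4. What would give 5.77.** A single band up to 40 nm wide would have to peak at 482-491 nm. At 451 nm it would have to be 87-90 nm wide. A mixture also works. If a share f of the lux is out of band, the ratio is f × r(leak) + (1 − f) × r(blue). Take FWHM 25 nm and a 32-year lens, so r(blue) = 16.77 and r(green) = 1.086:

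- Green leak: f = (16.77 − 5.77)/(16.77 − 1.086) = 0.70 of the lux, from about 13% of radiant power. Its share of EML is 0.70 × 1.086/5.77 = 13%.
- Red leak, with negligible melanopic effect: f = (16.77 − 5.77)/16.77 = 0.66 of the lux, from about 23% of radiant power.

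Over blue FWHM 15-40 nm and lens ages 20-45, the green leak is 10.5-13.8% of power, 62-73% of lux and 11.9-14.0% of EML. The red leak is 19.6-25.4% of power and 57-69% of lux.

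**5. Consequence under each explanation.**

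- *The blue lux is too high for a narrowband lamp, and EML 154 is right.* EML 154 needs 154/19.6 = 7.9 to 154/13.3 = 11.6 lux. Setting 26.7 lux would deliver 26.7 × 13.3 = 355 to 26.7 × 19.6 = 523 EML, or 2.3-3.4 times 154. With the 10-degree curve the factor is 1.2-1.6.
- *The luminaire adds out-of-band light.* The dose may be on target, but at a fixed 26.7 lux it is sensitive to the leak: 3 points less green power gives EML 182 (+18%), 3 points more gives 133 (−14%).
- *The EML cell is wrong.* Lux and dose stand.

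**6. From EML to the dose target.** CL_A/EML is 473.7/154 = 3.08 for blue and 473.7/274 = 1.73 for green. There is no fixed conversion, and the CL_A model is not in the documents, so the EML factors cannot be turned into CL_A or CS errors.

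**The case against.** The strongest reply is that no dose error has been shown. The targets are CL_A and CS; EML is a descriptive column that no hypothesis or model uses. Whether 26.7 lux of the installed source gives CL_A 473.7 cannot be tested from the documents. This stands in full.

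A modest green component from an RGB luminaire would reconcile every printed number and leave the peak at 451 nm. The protocol does not define narrowband, and Fig. 3 may show such a component. This also stands, and is why the point does not choose between the explanations. It does not dissolve the point: a source drawing most of its lux from outside the blue band is not narrowband in the usual sense, and with a green leak some 12-14% of the blue stimulus's EML would be light that Significance and Innovation treats as unattenuated by macular pigment.

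The green row fits about equally well with the standard and the 10-degree curve, so it cannot show which one Table 1 used. That is fair, and it narrows the gap to 6.8-9.2 without closing it.

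Finally, calibration to equal CL_A and spectrometer readings are already planned, and the lux values are marked approximate. True, but the only instrument named for calibration is the illuminance meter. The missing link is one sentence.

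**Conclusion.** The blue row's lux, its EML and the description as a narrowband 451 nm source cannot all be right: 5.77 is printed, against about 13-20 computed, or about 7-9 with a 10-degree curve. This rests on assumed photopic and melanopic curves, an assumed lens and Gaussian bands. Confidence is medium, and the point is a request for clarification.

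Three stronger readings are tempting and not supported.

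- That blue will be delivered at 2.3-3.4 times its intended dose: this is an EML figure, holds under only one of three explanations, and shrinks to 1.2-1.6 with the 10-degree curve.
- That the stated CL_A or CS is wrong: the model needed to test this is not given.
- That the MPOD-by-spectrum interaction or Aim 1 is undermined: a common blue offset cancels to first order between MPOD groups, and on-axis and off-axis conditions of one colour share the same target.

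What would be exposed, if the level is wrong, is the spectrum main effect and the green-versus-blue prediction in high-MPOD participants.

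**What to change.** Before the first session, measure both installed spectra at the chin rest with the spectrometer already listed. Set all four conditions to the common CL_A target from measured spectral irradiance, state this in the plan, and use the illuminance meter only as a drift check. Then recompute the lux and EML entries in Table 1 and the 27 lux figures in Experimental conditions and Fig. 5, and report any radiant power outside each band. If only the EML cell is wrong, correct that cell. Which explanation holds is for the sponsor to establish.

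Cost: about half a day of measurement (assumed) with listed equipment, a corrected table and one added sentence.
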